2.4 Study Flowchart

internal validation sample.

8. Phase 1: Refining of screening tests.
9. Phase 1: Processing of samples at ISCIII with extraction of DNA/RNA/antibodies from Whatman cards.
10. Phase 1: Screening tests on controlled samples from patients at HUIL.
11. Phase 1: Analysis of internal validation data.
12. Phase 1: Monitoring and quality control.
13. Phase 1: Reporting of results.
14. Phase 2: Education in prevention and training in screening for healthcare personnel.
15. Phase 2: Recruitment and collection of informed consent forms. Screening at Cañada Real Galiana. Sampling and sending of samples to ISCIII.
16. Phase 2: Processing of samples at ISCIII with extraction of DNA/RNA/antibodies from Whatman cards.
17. Phase 2: Screening tests on samples from subjects at Cañada Real Galiana.
18. Phase 2: Reporting of results to HUIL-Madrid Positivo.
19. Phase 2: Contact with patients who have tested positive.
20. Phase 3: Referral of patients to HUIL.
21. Phase 3: HCV diagnosis & treatment.
22. Phase 3: Follow up after HCV therapy.
23. Phase 3: Monitoring and control of baseline and final quality.
24. Cleansing of the epidemiological/clinical database and cross-referencing with laboratory data.
25. Statistical analysis.
26. Reporting of final results (congresses, papers, doctoral theses).
27. Drafting of the final report.

TASKS

1. HUIL: 1, 2, 3, 4, 5, 6, 7, 12, 19, 20, 21, 22, 23, 24, 25, 26, 27..
2. HRU Madrid Positivo/PH: 3, 4, 5, 6, 14, 15, 19, 20, 21, 22, 23.
3. ISCIII: 5, 6, 8, 9, 10, 11, 12, 13, 16, 17, 18, 23, 24, 25, 26, 27

KEY TO ABBREVIATIONS

AEMPS: Spanish Agency for Medicines and Medical Devices. CEIC: Clinical Research Ethics Committee. HUIL: Hospital Universitario Infanta Leonor (Infanta Leonor Teaching Hospital). ISCIII: Instituto de Salud Carlos III (Carlos III Health Institute).

FIGURE 2.4.1: INTERNAL VALIDATION TESTING AT HUIL

[figure not shown]

FIGURE 2.4.2: SCREENING IN CAÑADA REAL.

[figure not shown]

FIGURE 2.4.3: LAB TESTS IN ISCIII

[figure not shown]
[figure not shown]
[figure not shown]

FIGURE 2.4.5: COORDINATION

DURATION OF THE STUDY: 24 months

2.6 Study Duration

2.7 Statistical Analysis and Sample Size Justification

PHASE I

Once all subjects have been included, the results from the Whatman 903 cards will be compared with those obtained by venipuncture at HUIL. Diagnostic performance will be assessed by calculating the area under the ROC curve (AUROC) for each virus. The Se, Sp, PPV, and NPV for each virus will also be calculated.

PHASE II

Sample size: Assuming that around 10,000 people visit Cañada Real Galiana on different days, a sample size of 930 randomly selected subjects will suffice to estimate, with a 95% confidence interval and a precision of ± 3 percentage points, a

population percentage considered to be around 60%. A replacement rate of 0% has been anticipated.

PHASE III

In order to evaluate the effectiveness of the intervention, the accuracy of HCV tests will be calculated at the population level (AUROC, Se, Sp, PPV, and NPV), as will the percentage of patients arriving at the clinic, the percentage of patients treated, and the percentage of patients cured of hepatitis C. The incidence of HCV reinfection will be assessed using a Kaplan-Meier survival method. In addition, the effectiveness of the intervention for HIV, HBV, and HDV infection will be evaluated.

Statistical Methods

The statistical analysis will be performed using IBM SPSS Statistics for Windows, Version 22.0 (IBM Corp, Armonk, New York, USA) and the R statistical package, version 3.2.2 (GNU General Public License). All tests will be two-tailed, with p-values of <0.05 considered statistically significant.

An assessment will be performed to determine the percentage of patients who are positive at screening, are referred to a health center, have their diagnoses confirmed, and are treated at the end of the study. Factors associated with virus transmission, lack of referral to a health center, and HCV treatment will also be analyzed.

Continuous variables will be presented as mean and standard deviation; categorical data will be presented as absolute numbers and percentages. The prevalence (95% confidence interval) of antibody for HCV, HIV, and HDV, HBsAg, and active HCV infection will be calculated in the sample and in the subgroups studied. Categorical data and proportions will be analyzed using the chi-square test or Fisher exact test, as required. The *t* test, ANOVA, or Mann-Whitney test will be used to compare continuous variables. The association study will be performed using logistic regression and adjusting for the major epidemiological and clinical covariates.

VARIABLES INCLUDED

PHASE I: VARIABLES TO BE RECORDED DURING INTERNAL VALIDATION TESTING

- Date of birth
- Gender
- Date of sample collection
- Date of last analysis
- HCV antibody result from last analysis (positive/negative)
- HCV-RNA result from last analysis
- Genotype result from last analysis
- HIV antibody result from last analysis (positive/negative)
- CD4+ lymphocyte count for HIV-positive patients
- RNA-HIV result for HIV-positive patients
- HDV antibody result from last analysis (positive/negative)
- HBsAg result from last analysis (positive/negative)
- DNA-HBV result from last analysis
- Incidents or errors in sample collection (yes/no)

PHASE II: VARIABLES TO BE RECORDED DURING SCREENING

- Code allocated
- Date of sample
- Date of birth
- Gender (male/female)
- Nationality
- Homeless (yes/no)
- No. of days per week that the individual visits Cañada Real Galiana
- Drugs consumed (mark as relevant):
 - Heroin
 - Cocaine
 - Marihuana
 - Alcohol
 - Benzodiazepines
- Current use of parenteral methods (yes/no)
- Date when parenteral methods were first used
- Frequency of injections (daily [No. of times]/weekly [No. of times])
- Syringe sharing for >3 months (yes/no)
- Frequency of syringe sharing (daily/weekly/monthly)
- Date of switch from parenteral methods to smoking
- On methadone program (yes/no)
- Being monitored for HCV infection (yes/no)
- Have you previously been offered the chance to undergo HIV and/or HCV testing?
 - No
 - Yes, but I did not accept
 - Yes, with (positive/negative) results for HIV and (positive/negative) results for HCV
- Contact with health center (never, occasionally, regular monitoring).
 - Primary health care
 - Hospital
 - Drug abuse center
 - Other
- Advantages of alternative screening
- Drawbacks of alternative screening
- Contact data provided (yes/no)
- Post-test contact (yes/no)

PHASE III: VARIABLES TO BE RECORDED AFTER LABORATORY ANALYSIS

- HCV antibody result (positive/negative)
- HCV-RNA result
- Genotype result
- HIV antibody result (positive/negative)
- HIV-RNA result for HIV-positive patients
- HDV antibody result (positive/negative)
- HBsAg result (positive/negative)
- HBV-DNA result
- Incidents or errors in sample collection (yes/no)
- Referred to health center (yes/no)
- HCV antibody result from health center laboratory (positive/negative)
- HCV-RNA result from health center laboratory

	
 • Genotype result from health center laboratory • HIV antibody result from health center laboratory (positive/negative) • HIV-RNA result from health center laboratory • HBsAg result from health center laboratory (positive/negative) • DNA-HBV result from health center laboratory • Treated with antivirals (yes/no) • Grade of liver fibrosis (according to METAVIR or in kPa) • Regimen used for the treatment of HCV • Lost to follow-up (yes/no) • Duration of therapy • Sustained virological response at 12 weeks after finishing therapy (yes/no)

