
protocol.

The Whatman 903 cards used to collect whole blood will be handled by healthcare professionals. The device consists of a small card with five circles for collecting one drop of blood each. The card is attached to a record card where demographic information on the individual being tested is recorded. A small amount of capillary blood from the user's ring or middle finger is collected on the sample collection area and then allowed to dry at room temperature for three hours. The card is then made ready for transportation to the screening laboratory. It must be taken to the laboratory within 15 days of collection.

Samples will be sent to the CNM-ISCIH for laboratory testing. The cards will be stored at -80°C .

PHASE I: INTERNAL VALIDATION AND REFINING OF THE TECHNIQUE

Once the ethics committee has approved the study, samples will be obtained by finger pricking using Whatman 903TM cards at visits to the Internal Medicine department of HUIL. All patients visiting the department, for whom recent analytical data (serology results for HCV, HIV, HBV, and HDV, as well as HCV-RNA viral load and HCV genotyping collected during the previous 15 days) will be asked to take part in the internal validation study. Patients whose analyses were performed elsewhere or are not recent will not be included. Healthy individuals, i.e. those who have tested negative for HCV, HIV, HBV, and HDV will also be included. Individuals will be included in the validation consecutively until the preset number is reached (see below).

A total of 100 patients and 50 healthy individuals will be included to validate the screening test. Successive samples will be taken, and patients with genotypes 1a, 1b, 2, 3, and 4 will be included. National data indicate that the distribution of the most frequent genotypes in Spain is as follows: 1b, 44%; 1a, 26%; and 3, 20%. Therefore, these will be the genotypes most widely represented in our study. The 50 healthy individuals (negative for HIV, HBV, HCV, and HDV) will be obtained from the family members accompanying patients on medical visits, who will be invited to take part in the study. One dried blood sample will be taken by finger pricking and another simultaneous sample will be taken by venipuncture. The venipuncture sample will be processed through the usual channels at the center.

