Participants will be given an information leaflet and a specific informed consent form. Samples will be processed according to the study protocol (Annex 1). Clinical and epidemiological data will be recorded in a database that can be accessed by researchers from the HUIL and the CNM-ISCIH. The variables shown in section 2.4 will be recorded. This file has been included in the Register of Data Files of the ISCIH.

ELISA: A disc with a sample of dried blood will be placed in a microtube containing 300 μl of 0.5% buffer solution (PBS/BSA) and processed at $4-8^{\circ}\text{C}$ for 18-24 hours. After incubation, elutes from the dried blood samples will be tested for the presence of antibodies against HCV, HIV, and HDV, as well as for HBV surface antigen (HBsAg). Negative samples will not undergo further testing and will be considered non-infected. Positive samples will be tested using real-time PCR to confirm the positive results.

Real-time PCR: Nucleic acids will be extracted using the DSP virus pathogen kit (QIAGEN, Hilden, Germany). The samples will be stored at -80°C until use. A specific HCV test will be performed to confirm active HCV infection (HCV-RNA positive) on a Rotor Gene Q unit (QIAGEN).

PHASE II: SCREENING AT CAÑADA REAL GALIANA

Screening for HCV and the other viruses (HIV, HBV, and HDV) covered by this project will take place at Cañada Real Galiana. Screening will be conducted by nursing personnel hired specifically for that purpose. An active search will be made for

individuals who come into the shantytown from outside, and the detection test will be offered to everyone regardless of whether or not their serological condition is already known. Selection of individuals for screening will be random and consecutive.

Nursing personnel will generally be accompanied by an educator from the HRU. PWID will be offered information on prevention and the importance of early diagnosis and referral to health centers.

Information will then be provided on the goals of the study, and persons who agree to take part will be required to sign an informed consent form, provide contact data for subsequent location, and provide basic social and demographic data and information on their consumption habits. Regardless of whether or not individuals agree to take part in the study, they will all be given a card containing basic information on prevention and contact data for the internal medicine department of HUIL and the HRU.

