Hepatitis C therapy will be prescribed according to European and regional guidelines. Current guidelines recommend treating PWID independently of the liver fibrosis stage. In this project, antiviral therapy will be chosen regarding interactions with other drugs or methadone and a once-daily therapy is preferred in those patients who decline being referred to a detox centre.

After HCV therapy has been completed, all PWID will be periodically screened for hepatitis C (analyzing RNA HCV) to detect infection. Depending on the drug users risk factors, screening for reinfection of HCV will be carried out on a 3 to 6 months schedule.

Infanta Leonor Hospital (HUIL) is the reference specialized health centre for Cañada Real shantytown. All PWID diagnosed of HIV and HCV in this shantytown are referred to the HUIL internal medicine department for evaluation. The hospital is highly coordinated with the harm reduction unit. Nurses or doctors from the harm reduction unit accompany the patients to the specialized clinic.

ETHICAL ISSUES

All patients will sign an informed consent form. Confidentiality will be maintained with regard to personal and genetic data in accordance with the basic ethical principles for research involving biological samples and the provisions of applicable legislation (Organic Law 15/1999 of 13 December on Data Protection, Law 41/2002 on Patient and Healthcare Autonomy and Law 14/1986 on General Health). The ethical research principles set out in the Declaration of Helsinki and the Belmont Report will be adhered to, as will those of the UNESCO Universal Declaration on the Human Genome and Human Rights. The requirements of Spanish legislation on processing on personal data will also be met. The research project has been approved by the Research Committee at HUIL and the Ethics Committee of Hospital General Universitario Gregorio Marañón and ISCIII.

LIMITATIONS OF THE STUDY

The study may be limited by the possibility of not reaching the required number of subjects, although we believe this to be unlikely given the large number of people who visit Cañada Real Galiana. Furthermore, the limit of HCV detection by real-time PCR is approximately 1000 IU/mL, although we believe that with this limit we may detect the vast majority of active infections, since HCV viral load in untreated patients tends to be greater than 1000 IU/mL. Moreover, previous publications show 94% sensitivity and specificity for the Whatman card.

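### Phase I PPV and NPV will reflect the enrolment mix rather than Cañada Real, and Phase II prevalence intervals ignore card error; the effect depends on the marker and is small for HCV PPV and NPV

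*Combined protocol and SAP*

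**What the plan says.** **Phase I.** Section 2.3 fixes the validation sample: "A total of 100 patients and 50 healthy individuals will be included to validate the screening test". The patient group is defined by HCV type ("patients with genotypes 1a, 1b, 2, 3, and 4 will be included"); the numbers positive for HIV, HBsAg or HDV are not set. Section 2.7 adds: "The Se, Sp, PPV, and NPV for each virus will also be calculated". It states no prevalence at which PPV and NPV apply, and no rescaling.

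**Testing sequence.** The ELISA paragraph of section 2.3 says "Negative samples will not undergo further testing and will be considered non-infected" and "Positive samples will be tested using real-time PCR to confirm the positive results". The laboratory flowchart (Figure 2.4.3) is not readable in the copy reviewed.

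**Phase II.** Under Statistical Methods in section 2.7: "The prevalence (95% confidence interval) of antibody for HCV, HIV, and HDV, HBsAg, and active HCV infection will be calculated in the sample", and in subgroups. No adjustment for Se and Sp is described there or elsewhere in the readable text.

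**Accuracy known so far.** The limitations paragraph says that "the limit of HCV detection by real-time PCR is approximately 1000 IU/mL" and that "previous publications show 94% sensitivity and specificity for the Whatman card". The 94% is not tied to antibody, HBsAg or RNA.

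**Phase III.** Sections 2.3 and 2.7 plan to reassess HCV test accuracy in the target population, including PPV and NPV. Hospital confirmation is offered to those who screened positive.

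**The concern.** Se and Sp can be carried from a validation sample to another population if the spectrum of cases is similar. PPV and NPV cannot, because they change with prevalence. In Phase I the infected share is a product of recruitment: at most 67% for HCV, and whatever co-infection happens to occur for the other viruses. A reader who applied those predictive values to the shantytown would be using figures for a different population.

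The second half concerns Phase II. A card-positive proportion mixes true and false positives and omits missed cases. An interval based only on sampling error treats the card as perfect, although the protocol itself cites imperfect accuracy and Phase I will produce the estimates needed for a correction. Secondary objectives 4 and 5 (prevalence of active and resolved HCV, and of HIV, HBV and HDV) rest on these proportions.

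**Working it through.** **Inputs from the documents:** 100 patients and 50 healthy individuals; Se = Sp = 94%; Phase II n = 930, N = 10,000, expected 60%, ±3 points, 95%.

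**Assumptions:** 94% is applied to any marker for illustration; Sp of 98%, 99% and 100% are alternatives; true prevalences of 2%, 5% and 20% stand in for the rarer infections, because the documents give none.

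**1. The plan's own figure.** n0 = 1.96² × 0.6 × 0.4 / 0.03² = 1024.4. With the finite-population correction, 1024.4 / (1 + 1023.4/10,000) = 929.3, so 930. The figure reproduces. It allows for sampling error only.

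**2. Predictive values.** PPV = p·Se / [p·Se + (1−p)(1−Sp)] and NPV = (1−p)·Sp / [(1−p)·Sp + p(1−Se)], at Se = Sp = 94%:

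| Prevalence p | PPV | NPV |
|---|---|---|
| 66.7% (enrolment mix, if all patients are positive) | 96.9% | 88.7% |
| 60% (plan's expected value) | 95.9% | 91.3% |
| 20% (assumed) | 79.7% | 98.4% |
| 5% (assumed) | 45.2% | 99.7% |

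**3. What a crude proportion reads.** Apparent = p·Se + (1−p)(1−Sp). The last column is 1.96 × √[a(1−a)/930], where a is the apparent value, without the finite-population factor.

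| Se / Sp (assumed by marker) | True | Reads | Error (points) | Sampling half-width (points) |
|---|---|---|---|---|
| 94% / 94% | 2% | 7.8% | +5.8 | 1.7 |
| 94% / 94% | 5% | 10.4% | +5.4 | 2.0 |
| 94% / 94% | 20% | 23.6% | +3.6 | 2.7 |
| 94% / 98% | 2% | 3.8% | +1.8 | 1.2 |
| 94% / 98% | 5% | 6.6% | +1.6 | 1.6 |
| 94% / 98% | 20% | 20.4% | +0.4 | 2.6 |
| 94% / 99% | 2% | 2.9% | +0.9 | 1.1 |
| 94% / 99% | 20% | 19.6% | −0.4 | 2.6 |

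**4. HCV at 60%.** With single-step Se = Sp = 94%, the crude value is 0.6 × 0.94 + 0.4 × 0.06 = 58.8%, an error of −1.2 points. That is inside ±3, but coverage of the nominal 95% interval falls to about 88%. For active HCV after ELISA then PCR, taking Sp near 100% and Se 94%, it is 0.6 × 0.94 = 56.4%, an error of −3.6 points. Coverage is then about 36%.

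**5. Uncertainty in Se and Sp.** Exact 95% intervals would be 87.4% to 97.8% for Se at 94/100, and 83.5% to 98.7% for Sp at 47/50.

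**6. Interval after correction.** Corrected prevalence = (apparent + Sp − 1)/(Se + Sp − 1), with J = Se + Sp − 1 = 0.88.
- HCV at 60%, Se and Sp known: ±3.01/0.88 = ±3.4 points.
- Validation part: 1.96 × √[(0.6² × 0.0564/100 + 0.4² × 0.0564/50)/0.88²] = ±4.4 points, with 100 positives and 50 negatives. Together: √(3.4² + 4.4²), about ±5.5 points.
- A marker at 5%, Se = Sp = 94%, 50 negatives: Sp alone gives 1.96 × √[0.95² × 0.0564/50]/0.88 = ±7.1 points. Adding sampling error of 1.96/0.88 = ±2.2 points gives about ±7.4, so the interval reaches zero.

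**The case against.** **Phase III already plans accuracy in the target population.** This is true for HCV and must be credited: a reader might infer that the plan offers only enrolment-based PPV and NPV, and it does not. The answer is partial. Only screen-positives are offered confirmation, and the limitations paragraph expects many to decline. PPV is estimable among attenders; Se, Sp and NPV are not without verification-bias methods, and none are described. For HIV, HBV and HDV the plan promises an evaluation of effectiveness, not accuracy.

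**The 2:1 mix barely matters for HCV.** This stands. The shift is 1.0 point in PPV and 2.6 in NPV. The 67% is also an inference from fixed enrolment, and it applies at most to HCV.

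**The large biases rest on assumptions.** This also stands. A reader might infer that HIV, HBV and HDV prevalence will be inflated far beyond sampling error. The documents do not support that as a general statement: they give neither Se and Sp by marker nor expected prevalences. With Sp 99% the error is below the sampling half-width at 2% and 20%, and negative at 20%.

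**ELISA-positives are confirmed by PCR.** For active HCV this removes most false positives and turns the likely error into under-estimation, because ELISA-negatives are not retested and PCR has a detection limit. It does not settle the antibody and HBsAg prevalences, which are four of the five reported. A negative PCR does not show that an antibody result was false; objective 4 itself counts resolved HCV. Only an HCV-specific PCR is detailed, and the Phase III variable list has no HDV-RNA. Figure 2.4.3 might say more.

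**A correction built on as few as 50 assured negatives may be too imprecise to lead the report.** This is fair, and the fix allows for it.

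**Conclusion.** The point holds in limited form. As written, Phase I PPV and NPV describe the enrolment mix, and Phase II intervals ignore card error. For HCV PPV and NPV the practical effect is small. For rarer infections it can be large, but the figures of 45% PPV and 10.4% for a true 5% are illustrations under an assumed 94% for each marker, not predictions. For active HCV the more plausible error is downward: 56.4% for a true 60%, if serial testing has Sp near 100% and Se 94%.

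A reader might also infer that the corrected prevalence should replace the crude one as the main estimate. The documents do not support going that far: the validation sample assures only 50 negatives and sets no number of positives for three of the four viruses, so the choice trades bias against precision. The gap should be closed before analysis, but it affects mainly secondary objectives and the reading of Phase I, not the feasibility of the study.

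**What to change.** **Phase I.** Report Se and Sp per marker with exact 95% intervals and the numbers of positives and negatives behind them. Compute PPV and NPV by Bayes' rule at each marker's Phase II prevalence, or over a stated range, instead of from the enrolment mix.

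**Phase II.** Keep the crude prevalence. Beside it, as a sensitivity analysis, give a Rogan-Gladen or Bayesian corrected prevalence per marker. Use the Se and Sp of the whole testing algorithm for that marker, and carry Phase I uncertainty into the interval (for example by bootstrap). State for each marker whether PCR confirmation enters the definition of a positive.

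**Cost.** SAP text and a short program, with no new data. The price is wider corrected intervals: about ±5.5 points for HCV at 60% under the assumptions shown, and intervals that may reach zero for rare infections.

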In contrast with the rapid tests, sample processing is centralized, so results are not available immediately. Given that screening is performed in an unfavorable setting and on an outpatient basis, a series of problems could arise, as follows: (1) errors in the processing of samples (eg, insufficient sample volume contamination, loss); (2) difficulties in contacting participants once the results are available; and (3) the assumption that although a significant percentage of consumers will consent to screening, many will refuse referral to a health center for confirmation of diagnosis and treatment.

GENERAL TASKS

1. Administrative tasks: Classification by the Spanish Agency for Medicines and Medical Devices (AEMPS) and presentation to the Clinical Research Ethics Committee (CEIC).
2. Contracting of IT services. Design of online data collection forms.
3. Final design of protocol and informed consent forms.
4. Design of database and adaptation of online data collection forms.
5. Initial meeting of researchers.
6. Six-monthly teleconferences for researchers.
7. Phase 1: Recruitment, collection of informed consent forms, collection of

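### The Phase II precision of ±3 points assumes a random draw with no losses, but recruitment is consecutive and on site, so ±3 is not assured and prevalence may not describe all visitors

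*Combined protocol and SAP*

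**What the plan says.** The Phase II sample-size paragraph of section 2.7 starts from a finite population: "Assuming that around 10,000 people visit Cañada Real Galiana on different days". For an expected percentage of about 60% it states that "a sample size of 930 randomly selected subjects will suffice to estimate, with a 95% confidence interval" and a half-width of 3 points. On losses it says: "A replacement rate of 0% has been anticipated".

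Section 2.3, Phase II, describes an active search on site. The test is offered to everyone approached, and those who consent and give contact data take part. It adds: "Selection of individuals for screening will be random and consecutive". The visible text gives no list to sample from, no random mechanism and no scheme for sampling days or times. The limitations in section 2.3 foresee "errors in the processing of samples (eg, insufficient sample volume contamination, loss" among the likely problems.

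The Phase II variables in section 2.7 include "No. of days per week that the individual visits Cañada Real Galiana" and current injecting. The statistical methods plan prevalence with a 95% confidence interval in the sample and in subgroups. They mention no weighting and no design effect.

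**The concern.** The sample-size paragraph and the recruitment text describe different designs. A finite-population correction is earned by drawing at random from a defined population. Approaching whoever is present, one after another, is not such a draw, and calling it random as well as consecutive does not supply the mechanism. The zero loss allowance also sits badly beside the plan's own list of sample failures.

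The second issue is what the estimate describes. Someone who comes every day has more chances to be approached than someone who comes once a week. An unweighted percentage therefore leans towards frequent visitors. If they differ in infection status, it misses the prevalence among all visitors, and a larger sample would not cure that. Objective 6 repeats the prevalence estimate at 24 months. If frequency and infection are related, a change in visitor mix could then look like a change in prevalence.

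**Working it through.** **Inputs from section 2.7:** p = 0.60, half-width d = 0.03, z = 1.96 (95%), N = 10,000, n = 930, losses 0%.

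**The plan's own figure**
- Infinite population: n0 = 1.96² × 0.60 × 0.40 / 0.03² = 1024.4.
- With the finite-population correction: 1024.4 / (1 + 1023.4/10,000) = 929.3, rounded up to 930.
- Half-width at 930: 1.96 × √(0.24/930) × √(9070/9999) = ±2.999 points.

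So 930 reproduces and has no slack. Without the correction the requirement is 1025.

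**Precision when the assumptions are relaxed** (half-width = 1.96 × √(0.24/n), times the correction factor where stated)

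| Situation | Usable n | Half-width (points) |
|---|---|---|
| Plan's assumptions, with correction | 930 | ±3.00 |
| No correction | 930 | ±3.15 |
| 10% unusable cards (assumed), with correction | 837 | ±3.18 |
| 10% unusable cards (assumed), no correction | 837 | ±3.32 |
| Injectors only, 70% of sample (assumed), no correction | 651 | ±3.76 |
| Injectors only, 50% of sample (assumed), no correction | 465 | ±4.45 |

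The injector rows also assume 60% prevalence among injectors and no lost cards.

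**Visit frequency.** Section 2.3 gives 4000 to 6000 visitors a day. If the 10,000 of section 2.7 were a stable pool (an assumption), the average person would attend on 40% to 60% of days. Repeat visiting is therefore common. These figures do not show how widely frequency varies or whether it is related to infection.

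Assume half the visitors come often and half rarely, true prevalence is 60%, and the chance of enrolment is proportional to days per week:
- Same prevalence in both groups: bias 0.
- 5 versus 2 days, 65% versus 55%: (5 × 65 + 2 × 55)/7 = 62.1%, bias +2.1 points.
- 7 versus 2 days, 70% versus 50%: (7 × 70 + 2 × 50)/9 = 65.6%, bias +5.6 points.

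If rare visitors had the higher prevalence, the sign would reverse.

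**Price of weighting by 1/days.** The Kish design effect is mean(w²)/mean(w)² over the sample. For 7 versus 2 days, the sample shares are 7/9 and 2/9 and the weights 1/7 and 1/2:
- mean(w) = 1/9 + 1/9 = 0.2222.
- mean(w²) = 1/63 + 1/18 = 0.0714.
- Design effect = 0.0714/0.0494 = 1.45.

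If days 1 to 7 are equally common in the population, the design effect is 1.48. The weighted half-width is then 3.15 × √1.45 = ±3.79 with all 930 usable. With 837 usable and a design effect of 1.5 it is 3.32 × √1.5, or about ±4.1.

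**The case against.** The other side has a good deal of force.

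- A reader might infer that the prevalence will be biased upward, because daily visitors are plausibly the heaviest users. The documents do not support this. They contain no data linking visit frequency to infection, so neither direction nor size is known.
- A reader might infer that the study really delivers only ±4. For the planned unweighted estimate, the figures under these assumptions are ±3.15 to ±3.32. The wider figure comes mainly from the proposed weights and is a cost of the remedy.
- A reader might infer that the reported intervals will be too narrow. Section 2.7 promises a 95% confidence interval and does not say that the finite-population correction will be applied to it. An ordinary binomial interval would reflect the usable sample. What is shown to be optimistic is the planning figure.
- Subgroup prevalence is already planned and injecting status is recorded, so injectors are not ignored. What is missing is their naming as a subgroup with a stated precision.
- Figure 2.4.2, on screening at the site, is not reproduced in the text available and might describe selection. Only the visible text can be said to lack a mechanism.
- Prevalence falls under secondary objectives 4 to 6. The percentages referred, treated and cured do not depend on a random sample of 10,000 visitors.

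All of this stands, and it limits the point. It does not reconcile random selection and zero loss with consecutive recruitment and foreseen sample failure.

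**Conclusion.** The point holds in limited form and is a should-fix. The arithmetic behind 930 is right; the sampling and loss assumptions behind it are not supported by the visible recruitment text. The stated ±3 points is therefore not assured. The shortfall is modest: ±3.15 without the correction, and ±3.32 if 10% of cards, an assumed rate, are also unusable.

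Selection by visit frequency is a possible bias, not a demonstrated one. It needs two conditions: enrolment that rises with visit days, which on-site recruitment makes likely, and a relation between visit days and infection, on which the documents are silent. The examples of 0, +2.1 and +5.6 points show what different assumptions would produce and are not forecasts.

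**What to change.** 1. Reconcile section 2.3 with section 2.7. Call the sample consecutive unless a random mechanism is defined. Drop the finite-population correction and the zero loss allowance, and restate precision for 930 enrolled as about ±3.2 to ±3.3 points, with the assumed loss rate given.
2. Prespecify a sensitivity estimate of prevalence weighted by 1/(days per week visited), with a robust variance. Include a rule for people who visit less than weekly, since the weight is undefined if they are recorded as 0. State that the interval will be wider, about ±3.8 to ±4.1 points if the design effect is about 1.5. State also that the weights assume an equal chance of being met and consenting on each visit day, and do not correct for refusal.
3. Limit the unweighted estimate to people encountered and consenting. Report injectors as a named subgroup with its own precision: about ±3.8 points if 70% of the 930 inject and ±4.5 if 50% do, both shares being assumptions. The sponsor should define the subgroup in advance as current or ever injectors.

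The cost is revised wording and a few lines of survey-weighted code. Visit days and injecting status are already collected, and no extra participants are needed. The plan gives up a slightly tighter precision statement and a claim about all visitors that its visible design does not secure.
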